APPENDIX B: CLINICAL LABORATORY ANALYTES

Standard Safety Chemistry Panel

Alanine aminotransferase	Albumin
Alkaline phosphatase	Amylase
Aspartate aminotransferase	Bicarbonate
Bilirubin (total, direct, and indirect)	Blood urea nitrogen
C-Reactive Protein	Chloride
Calcium	Creatinine
Creatine kinase	Gamma-glutamyl transferase
Estimated glomerular filtration rate	Inorganic phosphorus
Glucose	Lipase
Lactate dehydrogenase	Sodium
Potassium	Uric acid
Total protein	Uric acid

Hematology

Hematocrit	Hemoglobin
Platelets	Red blood cell count
White blood cell count and differential [1]	

1. Manual microscopic review is performed only if white blood cell count and/or differential values are out of reference range.

Coagulation

Prothrombin time	International normalized ratio
------------------	--------------------------------

Urinalysis

Bilirubin	Blood
Glucose	Ketones
Leukocyte esterase	Microscopy [1]
Nitrite	pH
Protein	Specific gravity
Urobilinogen	

1. Microscopy is performed only as needed based on positive dipstick test results.

Other Tests

Urine pregnancy test (females of childbearing potential only)

APPENDIX C: APACHE II SCORE FORM

	Physiologic Variable	High Abnormal Range				0	Low Abnormal Range			
		+4	+3	+2	+1		+1	+2	+3	+4
1	Temperature rectal (°C)	≥41	39-40.9		38.5-38.9	36.0-38.4	34-35.9	32-33.9	30-31.9	≤29.9
2	Mean arterial pressure = (2 x diastolic + systolic)/3	≥160	130-159	110-129		70-109		50-69		≤49
3	Heart rate (ventricular response)	≥180	140-179	110-139		70-109		55-69	40-54	≤39
4	Respiratory rate (non-ventilated or ventilated)	≥50	35-49		25-34	12-24	10-11	6-9		≤5
5	Oxygenation A-aDO ₂ or PaO ₂ (mmHg) a)FiO ₂ ≥0.5 record A-aDO ₂	≥500	350-499	200-349		<200				
	b)FiO ₂ <0.5:record only PaO ₂					>70	61-70		55-60	<55
6	Arterial pH If no ABGs record serum HCO ₃ below	≥7.7	7.6-7.69		7.5-7.59	7.33-7.49		7.25-7.32	7.15-7.24	<7.15
7	Serum sodium	≥180	160-179	155-159	150-154	130-139		120-129	111-119	≤110
8	Serum potassium	≥7	6-6.9		5.5-5.9	3.5-5.4	3-3.4	2.5-2.9		<2.5
9	Serum creatinine (mg/dL) Double point for acute renal failure	≥3.5	2-3.4	1.5-1.9		0.6-1.4		<0.6		
10	Hematocrit (%)	≥60		50-59.9	46-49.9	30-45.9		20-29.9		<20
11	White blood count	≥40		20-39.9	15-19.9	3-14.9		1-2.9		<1
12	Glasgow Coma Scale (see next page) (Score = 15 minus actual GCS)	15 minus the GCS =								
A	Total Acute Physiology Score (APS)	Sum of the 12 individual variable points =								
*	Serum HCO ₃ (venous-mmol/L) Not preferred, use if no ABGs	≥52	41-51.9		32-40.9	22-31.9		18-21.9	15-17.9	<15

APPENDIX C: APACHE II SCORE FORM (CONT'D)

Glasgow Coma Scale (Circle appropriate response)		B Age Points	C Chronic Health Points	Apache II Score (sum of A+B+C)
Eyes open 4 - spontaneously 3 - to verbal 2 - to painful stimuli 1 - no response	Verbal - nonintubated 5 - oriented and conversant 4 - disoriented and talks 3 - inappropriate words 2 - incomprehensible sounds 1 - no response	Age ≤44 0 45-54 2 55-64 3 65-74 5 ≥75 6	If any of the 5 CHE categories below is answered with yes, give +5 points for non-operative or emergency postoperative patients or +2 points for elective postoperative patients.	A APS points (from prior page) + B Age points + C Chronic Health points _____ = Total APACHE II
Motor response 6 - to verbal command 5 - localizes to pain 4 - withdraws to pain 3 - decorticate 2 - decerebrate 1 - no response	Verbal - intubated 5 - seems able to talk 3 - questionable ability to talk 1 - generally unresponsive	Age points =	Liver Cardiovascular Pulmonary Kidney Immune	- Cirrhosis with PHT or encephalopathy - Class IV angina or at rest or with minimal self-care activities - Chronic hypoxemia or hypercapnia or polycythaemia of PHT >40 mmHg - Chronic peritoneal or haemodialysis - Immune compromised host
			Chronic Health Points =	

A-aDO₂ = alveolar-arterial oxygen difference; ABG = arterial blood gases; APACHE = Acute Physiology and Chronic Health Evaluation; APS = acute physiology score; CHE = chronic health evaluation; FiO₂ = fraction of inspired oxygen; GCS = Glasgow coma scale; HCO₃ = bicarbonate; IV = intravenous; PaO₂ = arterial partial pressure of oxygen; PHT = pulmonary hypertension.

Source: Knaus WA, Draper EA, Wagner DP, et al. APACHE II: a severity of disease classification system. Crit Care Med. 1985;13(10):818-29

APPENDIX D: DRUG-INDUCED LIVER INJURY CRITERIA

For patients with normal liver transaminases and bilirubin at baseline:

If patients with normal baseline liver indices develop new elevations of aspartate aminotransferase (AST) or alanine aminotransferase (ALT) or alkaline phosphatase (ALP) >3 x upper limit of normal (ULN) or total bilirubin (TBL) >2 xULN values during the study, repeat testing should be performed within 48 to 72 hours. Investigators should also ask the patient if he/she has symptoms.

If there are persistent elevations (ALT or AST >3 x ULN or TBL >2 x ULN) upon repeat testing, then close observation (as described below) should be implemented and discontinuation of drug should be considered.

Drug should be discontinued, and the patient followed until resolution of symptoms or signs in the following situations:

- ALT or AST >8 x ULN
- ALT or AST >5 x ULN for more than 2 weeks.
- ALT or AST >3 x ULN and (TBL >2 x ULN or INR >1.5)
- ALT or AST >3 x ULN with the appearance of fatigue, nausea, vomiting, right upper quadrant pain or tenderness, fever, rash, and/or eosinophilia ($>5\%$).

For patients with elevations in baseline transaminases or bilirubin:

If patients with abnormal baseline liver indices develop elevations of AST or ALT >2 x baseline or TBL >2 x baseline values during the study, repeat testing should be performed within 48 to 72 hours. Investigators should also ask to the patient if he/she has symptoms.

If there are persistent elevations (ALT or AST >2 x baseline or TBL >2 x baseline values) upon repeat testing, then close observation (as described below) should be implemented and discontinuation of drug should be considered.

Drug should be discontinued, and the patient followed until resolution of symptoms or signs in the following situations:

- If baseline measurements were <2 x ULN, discontinue if ALT or AST increases to >5 x baseline measurements.
- If baseline average measurements >2 x ULN, discontinue if ALT or AST increases to >3 x baseline measurements.
- Discontinue if ALT or AST increase >2 x baseline measurements AND the increase is accompanied by a concomitant increase in TBL to >2 x baseline measurements or the INR concomitantly increases by >0.2 .
- For any patients who present with a constellation of syndromes indicative of liver disease as per the Investigator's overall assessment (ie, fatigue, nausea, vomiting, right upper quadrant pain or tenderness, fever, rash, and/or eosinophilia [$>5\%$]).

Close observation for suspected drug-induced liver injury includes the following:

- Repeating liver enzyme (ALT, AST, and ALP) and TBL tests 2 or 3 times weekly. The frequency of repeat testing can decrease to once a week or less if abnormalities stabilize or the study drug has been discontinued and the patient is asymptomatic.
- Obtaining a more detailed history of symptoms and prior or concurrent diseases.
- Obtaining a history of concomitant drug use (including nonprescription medications and herbal and dietary supplement preparations), alcohol use, recreational drug use, and special diets.
- Ruling out acute viral hepatitis types A, B, C, D, and E; autoimmune or alcoholic hepatitis; hypoxic/ischemic hepatopathy; and biliary tract disease.
- Obtaining a history of exposure to environmental chemical agents.
- Obtaining additional tests to evaluate liver function, as appropriate (eg, INR, direct bilirubin).
- Considering gastroenterology or hepatology consultations.

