4.2 Exclusion Criteria

Participants who meet any of the following criteria will not be eligible for the study:

1. Blood culture, or any other culture, positive for *C. krusei*
2. Life expectancy of <7 days in the opinion of the Investigator
3. Severe or moderate hepatic impairment (Child-Pugh Score >6 points) at any time during 2 weeks prior to dosing. The Child-Pugh score of >6 is applicable to patients with hepatic dysfunction and cirrhosis only.
4. Baseline neurological conditions such as abnormal movements or convulsive disorders
5. Human immunodeficiency virus-infected patients who are receiving antiretroviral therapy that are moderate to strong inducers of CYP3A4, or who have detectable viremia, or who have had an active opportunistic infection within 6 months prior to Screening
6. Alanine aminotransferase or aspartate aminotransferase $\geq 5 \times$ upper limit of normal (ULN)
7. Total bilirubin $> 3 \times$ ULN, unless isolated hyperbilirubinemia or due to documented Gilbert's disease.
8. Female patient is pregnant or lactating
9. Inappropriate fungal infection source control (e.g. persistent indwelling catheters or intravascular devices)
10. Investigational drug administered within 30 days prior to dosing or five half-lives whichever is longer
11. Concomitant use of medication that is a strong inducer of CYP enzymes (e.g. rifampin, carbamazepine, phenytoin, rifabutin, efavirenz, nevirapine, phenobarbital, modafinil, nafcillin, St. John's Wort, and enzalutamide)
12. Any other condition or laboratory abnormality that, in the opinion of the Investigator, would put the patient at unacceptable risk for participation in the study or may interfere with the assessments included in the study
13. Diagnosis of deep-seated *Candida*-related infections causing hardware associated septic arthritis, osteomyelitis, endocarditis, myocarditis, hepatosplenic candidiasis, or a central nervous system infection or site of infection that would require antifungal therapy to exceed the maximal duration of study drug treatment (i.e. 6 weeks [42 days])

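### Appendix D does not give coherent ALT/AST stopping levels across eligible baselines: no ULN floor for bilirubin-only patients, an unnamed governing analyte, a step down across 2 x ULN, and a gap at exactly 2 x ULN

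*Protocol*

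**What the plan says.** Protocol Appendix D divides patients into two sets.

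The first is headed "For patients with normal liver transaminases and bilirubin at baseline". Its limits are in ULN units. A new ALT, AST or ALP above 3 x ULN, or bilirubin above 2 x ULN, calls for a repeat test. Drug is stopped at "ALT or AST >8 x ULN", at "ALT or AST >5 x ULN for more than 2 weeks", or at ALT/AST >3 x ULN combined with bilirubin >2 x ULN, INR >1.5 or listed symptoms.

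The second is headed "For patients with elevations in baseline transaminases or bilirubin". Its numerical limits are relative to baseline. ALT, AST or bilirubin above 2 x baseline calls for a repeat test; if that persists, close observation follows and stopping is to be considered. Four bullets then govern discontinuation:

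1. "If baseline measurements were <2 x ULN, discontinue if ALT or AST increases to >5 x baseline measurements"
2. "If baseline average measurements >2 x ULN, discontinue if ALT or AST increases to >3 x baseline measurements"
3. "Discontinue if ALT or AST increase >2 x baseline measurements AND the increase is accompanied by a concomitant increase in TBL" to above 2 x baseline, or by an INR rise of more than 0.2
4. A symptom picture judged by the investigator, with no ALT/AST level

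Section 4.2 excludes ALT or AST at 5 x ULN or more. It excludes total bilirubin above 3 x ULN, "unless isolated hyperbilirubinemia or due to documented Gilbert's disease". Patients with raised bilirubin and a normal ALT can therefore enrol, as can patients with ALT just below, at or just above 2 x ULN.

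The force of the rule varies. Section 8.1.1 makes withdrawal obligatory for DILI as Appendix D defines it. Section 4.4 lists significant DILI among reasons for which dosing may be stopped.

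**The concern.** Entry to the second set is by transaminases or bilirubin, but once a patient is in it every ALT/AST limit scales with that patient's own baseline, even if ALT and AST were normal. Nothing keeps such a limit above a minimum in ULN units. The switch from 5 x to 3 x baseline at 2 x ULN also makes the limit fall as the baseline gets worse, and the two inequalities do not meet.

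Patients are enrolled because they have limited antifungal options, so a stop that comes too early or too late matters for safety. A stop also fixes EOST, the time point of the primary endpoint. Under Section 7.4.1, giving another systemic antifungal straight after EOST for suspected or documented *Candida* infection rules out Treatment Success.

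**Working it through.** The plan states no derived figure to reproduce. The check converts each rule to ULN units.

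**Inputs.** b = baseline ALT (or AST) as a multiple of ULN. Eligible range b < 5 (Section 4.2). From Appendix D: normal-set ALT/AST-only stop at 8; normal-set repeat-test trigger at 3; bullet 1 = 5 x b for b < 2; bullet 2 = 3 x b for b > 2; bullet 3 (ALT/AST part) and the repeat-test tier = 2 x b.

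**Limits when ALT itself selects the bullet (all x ULN).**

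| Baseline b | Bullet | ALT/AST-only stop | 2 x b tier |
|---|---|---|---|
| 0.4 (bilirubin raised) | 1 | 5 x 0.4 = 2.0 | 0.8 |
| 1.1 | 1 | 5 x 1.1 = 5.5 | 2.2 |
| 1.9 | 1 | 5 x 1.9 = 9.5 | 3.8 |
| 1.99 | 1 | 5 x 1.99 = 9.95 | 3.98 |
| 2.00 | neither | none | 4.0 |
| 2.01 | 2 | 3 x 2.01 = 6.03 | 4.02 |
| 2.1 | 2 | 3 x 2.1 = 6.3 | 4.2 |
| Normal set | – | 8 | – |

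**No floor.** With raised bilirubin only and ALT 0.4 x ULN, bullet 1 stops drug at ALT >2.0 x ULN. Bullet 3 stops it at ALT >0.8 x ULN if bilirubin also exceeds 2 x baseline or INR rises by more than 0.2. With normal bilirubin, an ALT of 2.0 x ULN is below the repeat-test trigger of 3 x ULN.

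**Unnamed analyte.** Bullets 1 and 2 do not say whose baseline is compared with 2 x ULN. Take bilirubin 2.5 and ALT 0.4 x ULN, which is eligible. If ALT selects, bullet 1 gives 5 x 0.4 = 2.0. If bilirubin selects, bullet 2 gives 3 x 0.4 = 1.2.

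**Step at 2 x ULN.** From b = 1.99 to 2.01 the limit drops by 9.95 - 6.03 = 3.92 x ULN. Bullet 1 exceeds the normal-set limit of 8 once b > 8/5 = 1.6.

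**Gap.** Bullet 1 needs b < 2 and bullet 2 needs b > 2, so b = 2 has no ALT/AST-only limit.

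**Baseline term.** Bullet 1 refers to baseline measurements and bullet 2 to average ones. Appendix D defines neither.

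**The case against.** Several stronger readings are tempting, and the documents do not support them.

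- *The two sets contradict each other.* They are mutually exclusive, so no patient falls under both. The fault is incoherent levels, plus one ambiguity within the second set.
- *Raised bilirubin forces a stop at a normal ALT.* Bullet 1 alone does this only if baseline ALT is below 1/5 = 0.2 x ULN. At 0.4 x ULN, a stop within the normal range needs the bilirubin or INR condition of bullet 3.
- *A patient at 1.9 x ULN simply continues to 9.5 x ULN.* That figure is the ALT/AST-only backstop. Repeat testing starts above 3.8 x ULN, stopping is to be considered if the rise persists, bullets 3 and 4 may act earlier, and Section 8.5.2 lets the investigator stop for any laboratory abnormality.
- *Exactly 2 x ULN has no rule.* Only the ALT/AST-only limit is missing; the 2 x baseline tier and bullets 3 and 4 still apply.
- *A limit of 3 x 4.9 = 14.7 x ULN at baseline 4.9 is an error.* A higher absolute limit at a higher baseline is the ordinary result of baseline multiples and may be intended.
- *Bilirubin is uncapped at entry.* The bilirubin criterion has no ceiling for isolated cases, but exclusion 12 lets the investigator bar any laboratory abnormality judged an unacceptable risk.
- *SAP 7.1.3 settles the baseline.* It defines baseline for analysis of endpoints, not for a bedside stopping rule.
- *The primary result is biased.* An early stop is not automatically a Treatment Failure: a living patient with cleared cultures and no other antifungal can still be a success. With about 15 patients (Section 9.2.5), 1/15 = 6.7 percentage points is the weight of any one patient; the documents give no frequency for such stops.

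These points narrow the finding. They leave the missing floor, the unnamed analyte, the step, the gap and the two baseline terms untouched.

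**Conclusion.** The concern holds in this limited form and should be corrected. Read literally, Appendix D:

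- gives a bilirubin-only patient with ALT 0.4 x ULN a stop at >2.0 x ULN, or >1.2 x ULN if raised bilirubin (here 2.5 x ULN) selects the bullet;
- lowers the ALT/AST-only limit by about 4 x ULN as baseline crosses 2 x ULN, with no stated reason;
- sets 9.5 x ULN at baseline 1.9 against 8 x ULN for a normal baseline;
- leaves exactly 2 x ULN without an ALT/AST-only limit.

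The difference between Sections 4.4 and 8.1.1 adds doubt about whether a stop is binding; calling these stops mandatory rests on Section 8.1.1. The baseline values are illustrations within the eligible range, and the documents do not say how many patients would have them. An effect on the primary endpoint is possible, not shown.

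**What to change.** The sponsor should reconcile Appendix D, and Sections 4.4 and 8.1.1 (with the matching withdrawal text in the synopsis), so that:

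- each eligible baseline value, including exactly 2 x ULN, maps to one and only one ALT/AST-only limit;
- the analyte that selects the rule is named, including when only bilirubin or only transaminases are abnormal;
- the step across 2 x ULN is resolved or justified;
- one baseline term is used throughout and defined;
- the text says consistently whether meeting the criteria permits or requires withdrawal.

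The levels, their ordering and the baseline definition are for the sponsor's safety physician; none is proposed here. The cost is a short protocol amendment, about one page, with matching changes to any eCRF or alert checks. It needs no new procedures or patients.

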## LIST OF ABBREVIATIONS

Abbreviation	Definition
AE	Adverse event
ALT	Alanine aminotransferase
ALP	Alkaline phosphatase
APACHE	Acute Physiology and Chronic Health Evaluation
AST	Aspartate aminotransferase
ATC	Anatomical therapeutic chemical
BID	Twice daily
BMI	Body mass index
CSR	Clinical study report
CVC	Central venous catheter
DRC	Data Review Committee
DSMB	Data and Safety Monitoring Board
ECG	Electrocardiogram
eCRF	Electronic Case Report Form
EOST	End of Study Drug Treatment
ICF	Informed Consent Form
ITT	Intent-to-Treat
IV	Intravenous(ly)
LLN	Lower limit of normal
MedDRA	Medical Dictionary for Regulatory Activities
MITT	Modified Intent-to-Treat
PK	Pharmacokinetic(s)
PO	Oral(ly)
PP	Per-Protocol
QD	Once daily
SAE	Serious adverse event
SAP	Statistical analysis plan
SOC	Standard of care
spp.	Species
T2MR	T2 magnetic resonance
TEAE	Treatment-emergent adverse event
ULN	Upper limit of normal
WHO	World Health Organization

## 1 INTRODUCTION

The purpose of this Statistical Analysis Plan (SAP) is to provide a description of the statistical methods to be implemented for the analysis of data from the study with protocol number APX001-203. The SAP will be finalized prior to database lock. Any deviations from the SAP after database lock will be documented in the final Clinical Study Report (CSR).

## 2 STUDY OVERVIEW

### 2.1 Study Objectives

#### 2.1.1 *Primary Objective*

The primary objective of this study is to evaluate the efficacy and safety of APX001 for the treatment of adult patients aged 18 years and above, with candidemia and/or invasive candidiasis caused by *Candida auris*, who have limited antifungal treatment options.

#### 2.1.2 *Secondary Objectives*

The secondary objectives of this study are to:

- Evaluate the time to first negative blood culture;
- Evaluate the percentage of patients with successful Mycological Outcomes at End of Study Drug Treatment (EOST), and 2 and 4 weeks after EOST;
- Evaluate the percentage of patients with Treatment Success 2 and 4 weeks after EOST;
- Evaluate all-cause mortality at Study Day 30;
- Evaluate safety parameters, including number of patients with treatment-emergent adverse events (TEAEs); and
- Evaluate pharmacokinetic (PK) parameters of APX001.

### 2.2 Study Design

This is a multicenter, open-label, non-comparative, single arm study to evaluate the efficacy and safety of APX001 for the treatment of candidemia and/or invasive candidiasis caused by *C. auris* in patients aged 18 years and over with limited antifungal treatment options. Approximately 4-6 sites will be selected from the Republic of South Africa and Panama. The Study Drug Treatment Period will be up to a maximum of 42 days (inclusive of the loading dose [Study Day 1]). There will be a Follow up Period of 4 weeks (+4 days) after EOST. The total duration of participation in the study is up to approximately 10.5 weeks (inclusive of the Screening Period [ $\leq$ 168 hours prior to Baseline]). Patients must have had *C. auris* confirmed in culture  $<$ 120 hours (for candidemia) or  $<$ 168 hours (for invasive candidiasis without candidemia) prior to qualification and dosing in the study.

Screening and Baseline procedures will be performed within no more than 120 hours (for candidemia) or 168 hours (for invasive candidiasis without candidemia) from the time that the SOC blood and/or tissue sample or aspirate/fluid positive for *C. auris* was collected, and any outstanding baseline procedures completed before the first dose of study medication.

On Study Day 1 (or over the first 24 hours if dosing starts in the evening), a 1000 mg APX001 loading dose will be administered over 3 hours by IV infusion twice daily (BID). On Study Days

2 and 3, a 600 mg APX001 maintenance dose will be administered over 3 hours by IV infusion once daily (QD). On Study Day 4 and onward, the APX001 maintenance dose will be administered as either 600 mg APX001 IV infusion QD over 3 hours or 800 mg PO QD. Patients who have completed a minimum of 3 days of IV APX001, are clinically stable as determined by the Investigator, and are able to swallow tablets, may switch from IV to PO dosing on Study Day 4 and onward. Study drug will be administered for 14 days after clearance of *Candida* organisms from the bloodstream (two consecutive negative blood cultures), and in accordance with clinical judgment as applicable for other infected sites, up a maximum of 42 days.

Patients will be monitored by daily blood culture from signing informed consent, through dosing, during Study Drug Treatment until 2 consecutive blood cultures are negative for *Candida* spp., at EOST, and at 2 and 4 weeks after EOST, or Early Termination. For patients diagnosed with invasive candidiasis, relevant cultures, histopathology, and imaging tests to assess the site(s), extent, progress, and outcome of the *Candida* infection will be conducted as clinically indicated. All results should be recorded in the electronic Case Report Form. The management of intravascular catheters, intravascular devices, and, if applicable, any drains will be recorded, including any associated microbiology results.

Patients will be monitored for safety throughout the duration of the study. Safety assessments will include vital signs, clinical laboratory assessments (serum chemistry, hematology, coagulation, and urinalysis), physical examinations, neurological assessments (twice weekly on treatment), prior and concomitant medication reporting, and adverse event reporting. A 12-lead electrocardiogram (ECG) will be performed at Baseline (pre-dose), EOST, and 4 weeks after EOST, or Early Termination. A dilated fundoscopic examination will be performed at least once during the baseline period, which exclusively for this assessment may be up to Day 3 of the study. Follow-up fundoscopic examinations are required at EOST, and 4 weeks after EOST, or Early Termination for those patients who had positive findings up to Day 3 (or more if clinically indicated). A urine pregnancy test (for females of childbearing potential only) will be performed at Screening and Baseline (pre-dose), every 30 days during treatment if required by local regulations, at EOST, and 2 and 4 weeks after EOST, or Early Termination.

[figure not shown]
In the event of an inadequate response/failure on APX001 study treatment, the study drug may be discontinued and alternative antifungal treatment instituted.

Plasma samples for PK (APX001 [prodrug] and APX001A [active moiety]) will be collected at Baseline (pre-dose), twice weekly during Study Drug Treatment, and at EOST, 2 weeks after EOST, or Early Termination. Plasma samples for PK will be collected at the same time as samples are collected for the study's clinical laboratory assessments. Serum samples for (1,3)- $\beta$ -D-glucan levels will be collected at Baseline (pre-dose) and EOST, or Early Termination (if applicable).

The evaluation of treatment outcome will be assessed at EOST, and 2 and 4 weeks after EOST, or Early Termination.

The end of study will occur after the last visit of the last patient on the study.

A schematic representing the study's design is below and a complete schedule of procedures for the study is found in Table 1:

\*APX001 IV or PO QD

Maintenance Dosing

For patients with invasive candidiasis, maintenance dosing will continue until at least one negative tissue culture or aspirate/fluid

For patients with a deep-seated site of infection from which a tissue culture is not obtainable, maintenance dosing should continue until after the resolution of the attributable clinical signs of infection recorded at Baseline, and, as applicable, radiological improvement associated with the site of infection  
*maximum 6 weeks (42 days)*

